PROTOCOL TITLE: Implementation of Telemedicine for patients with wounds and ulcers.

1) Protocol Title

Title: Implementation of Telemedicine for patients with wounds and ulcers.

Protocol Version Date: March 11th, 2021

2) Objectives:

The objective of this quality improvement project is to assess if telemedicine can improve the quality of specialty care offered for new patients with wounds and ulcers due to peripheral artery disease (PAD) and diabetes mellitus (DM) at RHCs. The specific aims of this project are:

- a) Implement telemedicine consultations at rural health clinics.
- b) Evaluate the effect of telemedicine consultation to improve time to specialist evaluation and time to definitive treatment for patients with wounds and ulcers in rural clinics.
- c) To determine if patients with lower levels of activation need more resources to help get care when offered telemedicine

Hypothesis: *Telemedicine consultation can decrease mean time to specialist consultation and time to definitive vascular treatment by 50%. Use of telemedicine will be able to overcome low levels of patient activation by allowing patients to get care in their home area.*

3) Background

Each year, more than 185,000 patients with PAD, DM, or combined PAD/DM undergo leg amputation. Costs to treat wounds and ulcers currently approach \$25 billion annually and are expected to double in the next decade.^{1,2} When ulcer treatment is not effective, amputation is the outcome and currently, 1.4 million people live with an amputation in the United States.^{3,4} Predictors of higher amputation rates include worse ankle-brachial index,⁵ African-American race⁶, lower socio-economic status, dialysis dependence, and older age.⁷⁻¹⁰ Patients living in rural areas are 51% more likely to undergo amputation than those in urban areas.^{11,12}

Patients residing in rural areas face numerous barriers to care. Their concerns are poorly understood, however, these patients are typically of lower socioeconomic status and have limited knowledge of chronic diseases which results in lower patient activation. The distance and burden of coordinating travel, time off work, and need to attend multiple clinic visits can be impossible for patients and families. The hardships patients endure in an effort to attend remote appointments results in unrealistic patient expectations, physician dissatisfaction, non-compliance with treatment, increased hospitalizations, and lower patient activation in disease management.

In February 2016 focused guidelines for assessment of ulcers were published as a joint effort by the Society for Vascular Surgery, American Podiatric Medical Society, and Society of Vascular Medicine. Implementation of these guidelines

PROTOCOL TITLE: Implementation of Telemedicine for patients with wounds and ulcers.

has been poor, especially in rural areas. Telemedicine improves access to expert specialty consultation and patient-centered care in the ambulatory settings. Implementation of telemedicine combines involved faculty with a team-building mentality, concise web-based tools for incorporation into daily practice, and specialty consultation. Telemedicine has been effective in psychiatry, pediatrics, dermatology, and cardiovascular diseases. In telemedicine wound programs for the treatment of ulcers in other countries, physicians found images at remote consultation showed a high concordance compared to in-person evaluation and providers were successful at making wound care recommendations based on images.

The NHLBI strategic vision prioritized community-based effectiveness and implementation research strategies to address health inequalities. Multiple countries have implemented telemedicine wound care programs to improve cost effectiveness of treatment. These programs decreased costs for transportation to provide wound care by 46%. Extrapolation to US wound care costs could indicate a potential savings of nearly \$15 billion annually by implementing a national telemedicine treatment program for ulcer management.

The Vascular Clinic at UC Davis currently conducts telehealth medical visits as a part of the general referral program at UC Davis Health. Within this referral program the clinic works with several Rural Health Centers (RHC) in California and utilizes telehealth medicine as a part of the referral process. This research study proposes to examine the information that is collected during these visits the primary endpoint for this study is time to specialty consultation

4) Inclusion and Exclusion Criteria

Patients will be identified by the clinic when they come in for their regular visit.

Inclusion Criteria

1. 18 years or older
2. Have a wound or ulcer for more than two weeks.
3. Have a diagnosis of Diabetes Mellitus (DM), Peripheral Artery Disease (PAD), vascular disease, or combined PAD/DM
4. Willing to see a provider by telemedicine
5. Able to complete the Patient Activation Measurement (PAM) survey
6. Willing to be contacted by research team

Exclusion Criteria

1. Patients who do not want to participate in the telemedicine visit
2. Adults unable to read and write English. The PAM study is only in English at this time
3. Patients that do not have a home phone or home internet. This is needed to do follow up and any follow up telemedicine visits
4. Patients that do not have a smart phone or computer that can connect to the internet

PROTOCOL TITLE: Implementation of Telemedicine for patients with wounds and ulcers.

We do not plan to include:

- Pregnant women- low incidence of wounds in these patients due to PAD and DM
- Prisoners- Cannot accurately determine care and outcomes

Number of Subjects:

Rural Health Clinic A	25
Rural Health Clinic B	25
Rural Health Clinic C	25
Rural Health Clinic D	25
Rural Health Clinic E	25
Total Number of Patients	125

We plan to include 25 subjects at each of the 5 out of network clinics that are referred to the UC Davis Vascular Clinic for telehealth services for a total enrollment of 125 patients.

5) Study Timelines

The Screening and follow up of data of all patients will start approximately from 5/01/2020 – and end 12/31/2021

Review and Analysis should will be completed by approximately 06/30/2022

6) Study Endpoints

The primary endpoint for this study is time to specialty consultation.

Secondary endpoints are time to revascularization, time to other specialty consultation, time to wound healing, number of telemedicine visits, major amputation, number of hospitalizations, number of emergency room visits, and number of in person visits.

PROTOCOL TITLE: Implementation of Telemedicine for patients with wounds and ulcers.

7) Procedures Involved

Screening: Patients referred from rural clinics will be screened when they are referred to the UC Davis Vascular Clinic for telehealth services to determine if they meet the inclusion/exclusion criteria.

Enrollment/Procedures at Baseline Telehealth Visit: Patients receiving telehealth services will follow the standard operating procedures for those visits. Which includes asking new patients to complete the UCD Privacy statement for new patients and a patient activation questionnaire on the day of their telemedicine visit.

Follow-Up Post Telehealth Visit: All patients will be contacted every 4 weeks to determine if they have had a procedure for their leg wound (revascularization) and if the wound has healed. Patients will be followed until they reach a secondary study end-point which is wound healing, amputation, or for a maximum of 12 months.

8) Withdrawal of Subjects

Patients who choose not to participate in completing a patient activation questionnaire will not be included in this QI project. Patient care is not directed in this project and is clinical driven per standard of care and standard operating procedures for the Vascular Clinic.

9) Risks to Subjects

This is a minimal risk study and the only risk foreseen is a potential breach of confidentiality which will be minimized by securing the data as outlined in the protocol.

10) Potential Benefits to Subjects

No direct benefits to the patient will occur during the data collection and review of the QI project. Future patients may receive a benefit from increased access to telehealth visits or proven to shorten time to care for patients referred from rural clinics.

PROTOCOL TITLE: Implementation of Telemedicine for patients with wounds and ulcers.

Statistical Analysis Plan: Changed as a result of COVID and removal of the comparison arm of the study

The data will be analyzed by Kaplan-Meier analysis comparing time to specialty visit for patients who underwent telemedicine visits to those who did not. Secondary outcome analysis will include chi-squared analysis of the proportion of patients that had wound healing in the telemedicine group compared to those that did not have a telemedicine visit, and Kaplan-Meier analysis of time to definitive revascularization and wound healing for patients that underwent telemedicine and were treated at UCD.

Assuming a historical median time to a specialist consultation of 9 weeks, we will utilize a one-sample log-rank test. We want a sample large enough to detect a hazard ratio (HR) of 3.0 or higher. An HR of 3.0 indicates that at any time, three times as many specialists will consult many patients with telemedicine consultations compared to in-person consultations. A two-sided, one-sample log-rank test calculated from a sample of 24 individuals achieves 89.2% power at a 0.05 significance level to detect a hazard ratio of 3.0 when the median time to consultation of the historical control group is 9 weeks. The probability that a patient experienced a specialist consultation during the study is 0.44. The expected number of events during the study is 11. The time to specialist consultation is likely distributed by the Weibull distribution (shape parameter 1) by both groups (telemedicine and historical controls).

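### Patients selected for connectivity, English literacy, willingness and survey completion are tested against a 9-week historical median not stated to be restricted in the same way, so any selection difference would be read as a telemedicine effect

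*Combined protocol and SAP*

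**What the plan says.** **Who is enrolled.** Section 4 (Inclusion and Exclusion Criteria) requires willingness to be seen by telemedicine and ability to complete the Patient Activation Measurement survey. It excludes people who are not literate in English and two groups defined by connectivity: "Patients that do not have a home phone or home internet. This is needed to do follow up and any follow up telemedicine visits", and "Patients that do not have a smart phone or computer that can connect to the internet". Section 8 (Withdrawal of Subjects) leaves out anyone who declines the activation questionnaire.

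**What they are compared with.** The heading of the Statistical Analysis Plan says the comparison arm was removed. The sample-size paragraph then states: "Assuming a historical median time to a specialist consultation of 9 weeks, we will utilize a one-sample log-rank test". No source, period, population or eligibility is given for the 9 weeks. No matching, adjustment or sensitivity analysis is planned.

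**How the result is to be read.** The same paragraph explains a hazard ratio of 3.0 as meaning that "three times as many specialists will consult many patients with telemedicine consultations compared to in-person consultations". It is read as a contrast between two modes of consultation.

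**The concern.** A one-sample log-rank test takes the reference hazard as known and as the hazard the enrolled patients would have had without the intervention. Here that means assuming that connected, English-literate, willing survey completers would have waited a median of 9 weeks for an in-person specialist. The plan gives no reason to think so. If such patients would have been seen sooner anyway, the head start enters the hazard ratio and is reported as benefit.

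More patients do not help. The bias is fixed while the standard error shrinks, so moving from the 24 patients in the power statement to the 125 planned under Number of Subjects makes a false positive more likely. The problem remains even if 9 weeks is exactly right for the historical population, because an accurate figure for different patients is still the wrong reference.

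The reach of the conclusion is also at stake. The Objectives concern patients with wounds at rural health clinics generally, but the result would describe the subset passing these filters.

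**Working it through.** **Inputs from the plan (SAP, sample-size paragraph; Number of Subjects).** Historical median 9 weeks; hazard ratio 3.0; exponential times (Weibull, shape 1); 24 patients; two-sided 5%; event probability 0.44; 11 expected events; stated power 89.2%; planned enrolment 125.

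**Step 1: reproduce the stated power.**
- Null hazard: λ0 = ln2/9 = 0.0770 per week. At hazard ratio 3.0, λ1 = 0.2310.
- The plan gives no observation time for the primary endpoint. Solving 1 − exp(−λ1·T) = 0.44 gives T = 0.5798/0.2310 = 2.51 weeks per patient.
- Observed events per patient v1 = 0.44; null-expected events per patient v0 = 0.44/3 = 0.1467.
- Variance of O − E per patient under the alternative: v1 − (v1 − v0)² − 4·v00, where v00 = (1/9)[1 − 0.56 × 1.5798] = 0.0128. This is 0.44 − 0.0860 − 0.0512 = 0.3027.
- Power = Φ[(√24 × 0.2933 − 1.96 × √0.1467)/√0.3027] = Φ(0.6864/0.5502) = Φ(1.25) = 89.4%. At T = 2.49 weeks (event probability 0.437) it is 89.2%.
- Expected events: 24 × 0.44 = 10.56, rounded to 11.

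The plan's arithmetic is sound. It depends on 9 weeks being the enrolled patients' own median without telemedicine.

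**Step 2: let selection alone act.** Assume telemedicine has no effect and the eligible patients' own in-person median is m weeks. The plan gives no value for m, so 8, 7.5, 7 and 6 are assumptions, equivalent to hazard ratios 9/m of 1.125, 1.2, 1.29 and 1.5. Times were simulated as exponential with median m and censored at T, with E = Σ(ln2/9 × time), z = (O − E)/√E, and benefit declared if z > 1.96 (nominal 2.5% in that direction).

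| Patients | Observation | m = 9 | 8 | 7.5 | 7 | 6 |
|---|---|---|---|---|---|---|
| 125 | 2.5 weeks | 3% | 10% | 17% | 28% | 60% |
| 125 | 12 weeks | 3% | 20% | 40% | 65% | 97% |
| 125 | 52 weeks | 3% | 27% | 54% | 81% | >99% |
| 24 | 2.5 weeks | 4% | 8% | 10% | 13% | 24% |
| 24 | 52 weeks | 4% | 11% | 17% | 26% | 54% |

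**Step 3: check one cell by hand.** For m = 6, T = 2.51 and 125 patients, event probability is 1 − exp(−0.1155 × 2.51) = 0.252. So O ≈ 31.5, E ≈ 31.5/1.5 = 21.0, and z ≈ 10.5/√21.0 = 2.29, above 1.96. With 24 patients O ≈ 6.04, E ≈ 4.03 and z ≈ 1.00. The typical z grows by √(125/24) = 2.28, which is why the larger sample makes matters worse.

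**Step 4: effect on the estimate.** Selection multiplies the hazard ratio. A selection ratio of 1.5 and a true telemedicine ratio of 2.0 would together look like the design value of 3.0.

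**The case against.** Several points against the concern stand and limit it.

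- **The historical group is undescribed, not known to be unrestricted.** A reader might infer that the 9-week patients were unselected. The text supports only that matching is not stated. Filters tied to telemedicine willingness and the survey are, though, unlikely to have applied to in-person patients.
- **The direction of bias is not documented.** A reader might take the Background to say that rural delay comes from low status, limited knowledge and low activation. It says "these patients are typically of lower socioeconomic status and have limited knowledge of chronic diseases which results in lower patient activation", a statement about activation. The obstacles it names to attending remote visits are distance, travel, work and repeated appointments, which owning a smartphone does not remove. Those willing to use telemedicine might be the people for whom travel is hardest, and the bias would then run the other way. Patients must be able to complete the survey, not score well on it.
- **The 52-week figures should not stand alone.** The 12-month maximum in Section 7 governs follow-up after the telehealth visit, so it starts after the primary event. The 0.44 event probability implies about 2.5 weeks, where the rates are lower.
- **Selection alone would rarely imitate the full hypothesised effect.** With 125 patients and a 6-week median, the observed-to-expected ratio reaches 2 in about 0.1% of trials (52 weeks) to 4% (2.5 weeks). That limits the apparent size of effect, not the chance of a significant result, and the ratio is much less stable with 24 patients.
- **The device exclusion is not shown to be unnecessary.** Because aim (a) is to "Implement telemedicine consultations at rural health clinics", a reader might conclude that Section 4 should be relaxed. But the plan justifies home connectivity by follow-up and later telemedicine visits, counts telemedicine visits as a secondary endpoint, does not say how the four-weekly contact is made, and states in Section 8 that the project does not direct care. The documents do not support calling these exclusions errors.

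None of this supplies a reason why 9 weeks is the right reference for the enrolled patients. Nor does the Kaplan-Meier comparison with patients who had no telemedicine visit, still described in the SAP: the eligibility rules enrol no such patients, and that text needs reconciling with the one-sample test.

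**Conclusion.** The concern holds as a problem of comparability and interpretation. The primary test cannot separate selection from telemedicine, and the plan neither defines its benchmark nor examines the sensitivity of the result to it.

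If selection shortened the in-person median by one to three weeks, false declarations of benefit at 125 patients would run from about 10% to 60% (2.5 weeks of observation) or 27% to over 99% (52 weeks). At 24 patients they would run from about 8% to 24%, or 11% to 54%. These figures rest on exponential times, a single censoring time for all patients, no telemedicine effect, and assumed medians below 9 weeks. They show how the test responds if such selection exists, not that it exists. Because size and direction are unknown, the point merits a change to the analysis and wording but does not show that a positive result would be false.

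**What to change.** 1. **Define the benchmark.** State the source, period and population of the 9-week median. Where records allow, recompute it after applying every criterion a chart can show: age, wound longer than two weeks, a diabetes, PAD or vascular diagnosis, English, and a phone on record. Use the result as the null in the one-sample test.
2. **Add a sensitivity analysis.** Willingness, device ownership and survey completion cannot be matched from charts. Repeat the test with lower reference medians, for example 8, 7 and 6 weeks, and report the median at which significance is lost. No new data are needed: if E is the expected count at 9 weeks, the count at reference median m0 is E × 9/m0. For a result exactly as designed (24 patients, O = 10.56, E = 3.52), z is 7.04/√3.52 = 3.75 at 9 weeks and 5.28/√5.28 = 2.30 at 6 weeks. Significance is lost where the expected count reaches 5.83, at m0 = 31.68/5.83, about 5.4 weeks.
3. **Narrow the claim.** Describe the hazard ratio and conclusion as telemedicine users meeting these criteria versus historical in-person referrals, not as the effect of telemedicine in rural patients.

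The cost is a modest chart review (harder if historical records sit at the out-of-network clinics), a possibly shorter reference median with less power, one extra table and a more modest claim. Eligibility does not change. If the chart review proves impossible, items 2 and 3 and a plain description of the 9-week population are still feasible.

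### With one closing date for screening and follow-up and no last-enrolment date, the crude proportion healed mixes unequal follow-up and would understate 12-month healing if enrolment ran past 12/31/2020

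*Combined protocol and SAP*

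**What the plan says.** - **Section 5 (Study Timelines):** "The Screening and follow up of data of all patients will start approximately from 5/01/2020", with the end given as 12/31/2021. Screening and follow-up share this window. No last-enrolment date is given, and analysis is to finish by about 06/30/2022.
- **Section 7 (Procedures Involved, follow-up after the telehealth visit):** "All patients will be contacted every 4 weeks", and "Patients will be followed until they reach a secondary study end-point which is wound healing, amputation, or for a maximum of 12 months".
- **Statistical Analysis Plan:** two analyses of healing are planned. One is a "chi-squared analysis of the proportion of patients that had wound healing in the telemedicine group" against patients without a telemedicine visit. The other is a "Kaplan-Meier analysis of time to definitive revascularization and wound healing for patients that underwent telemedicine" and were treated at UCD. The first has no time point and no rule for patients whose follow-up is ended by the calendar.
- **Section 1:** "Protocol Version Date: March 11th, 2021". Section 7 of this version still describes screening in the future tense.

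**The concern.** The window and the follow-up rule fit together only for patients enrolled by 12/31/2020. After that date, how long an unhealed patient is observed depends on when the patient was referred. A crude proportion treats a patient unhealed after two months the same as one unhealed after twelve.

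Two things are at stake. The reported proportion healed would have no fixed meaning, because it would fall as accrual ran later even if healing were unchanged. The chi-squared comparison could also reflect a difference in length of follow-up rather than in healing, if the comparison patients were observed for longer or shorter than the telemedicine patients.

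**Working it through.** **The plan's own figures.** The documents give no healing rate, accrual rate or dropout rate, so there is no stated healing figure to reproduce. The only power statement concerns time to specialty consultation. Its event count follows from its inputs (24 × 0.44 = 10.56, rounded up to 11). A one-sample log-rank calculation with exponential times and null variance equal to the expected events gives power of 0.894 to 0.900, against the stated 89.2%. None of this depends on healing follow-up.

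**Dates (from sections 1, 5 and 7).**

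- Window: 5/01/2020 to 12/31/2021 = 609 days = 20.0 months.
- Part of the window that leaves a full 12 months: 5/01/2020 to 12/31/2020 = 244 days; 244/609 = 40%.
- If accrual were uniform over the whole window (assumed), the other 60% would have less than 12 months available: 0.599 × 125 = 75 patients.
- A patient enrolled on the version date has 295 days = 9.7 months. That allows 295/28 = 10 complete four-weekly contacts, against 365/28 = 13 in a full year.

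**Effect on the crude proportion.** Assumptions: uniform accrual from 5/01/2020 to month A; data cut at month 20; constant-hazard healing with true 12-month probability p; patients not seen to heal counted as not healed. Let λ = −ln(1 − p)/12. Patients enrolled in the first 8 months have 12 months available, and one enrolled at month t > 8 has 20 − t. For A from 8 to 20:

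crude = [8p + (A − 8) − (e^(−λ(20−A)) − e^(−12λ))/λ] / A

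Example, p = 0.60 and A = 20: λ = 0.9163/12 = 0.07636. Crude = [4.8 + 12 − (1 − 0.4)/0.07636]/20 = (16.8 − 7.858)/20 = 0.447, a shortfall of 15 points.

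| Accrual ends | True 40% | True 60% | True 80% |
|---|---|---|---|
| Month 8 (about 12/31/2020) | 40% | 60% | 80% |
| Month 12 | 38% | 58% | 78% |
| Month 14 (about 06/30/2021) | 36% | 55% | 75% |
| Month 17 | 33% | 51% | 70% |
| Month 20 (12/31/2021) | 29% | 45% | 62% |

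The shortfall is nil in the first row. In the last row it is 11, 15 and 18 points.

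**Effect on Kaplan-Meier.** Under the same assumptions, 1,500 simulated trials of 125 patients gave these mean 12-month estimates for true healing of 40/60/80%: 40.0/60.0/80.0% with accrual to month 14, and 39.9/60.1/80.2% with accrual to month 20. The calendar cut-off adds essentially no bias.

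**The case against.** The case against has five parts.

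- **Twelve months is a maximum.** Shorter follow-up does not contradict it, and patients who heal or have an amputation before the cut-off lose nothing. This stands. The point concerns only patients still unhealed at the cut-off.
- **Late enrolment is not documented.** The version date makes it plausible, but no accrual dates are given and the section 5 dates are approximate. If accrual ended by 12/31/2020 the bias is zero. This also stands, so the size must be given as a range.
- **Healing already has a suitable analysis.** The Kaplan-Meier analysis handles staggered entry and a calendar cut-off. This is right for that analysis, but the SAP plans the chi-squared test as well and does not say that the curve takes precedence.
- **The SAP never says that cut-off patients count as not healed, nor calls the proportion a 12-month outcome.** True, but counting them so is the plain reading of a crude proportion. Dropping only the unhealed ones would err in the other direction.
- **12/31/2021 might be the end of screening only.** Follow-up could then run to 12/31/2022, six months after analysis is due to finish, so this reading does not reconcile the dates.

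A reader might infer more: that healing will certainly be understated, and that revascularization and amputation results are biased too. The documents do not support this. Revascularization is to be analysed only by Kaplan-Meier, and no amputation proportion is specified. Nor is bias in the treatment comparison shown. It depends on the follow-up of patients without a telemedicine visit, which is not described, and the SAP heading says the comparison arm was removed.

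**Conclusion.** The concern holds in a limited form. Sections 5 and 7 allow follow-up of unequal length, and one secondary analysis, the crude proportion healed, is not protected against it. As a 12-month figure it would be too low by 0 points if accrual ended by 12/31/2020, and by up to about 15 points at 60% true healing if accrual ran uniformly to 12/31/2021. Over true healing of 40 to 80% the range is 0 to about 18 points. The accrual pattern, the constant hazard and the healing rates are assumptions.

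If the comparison patients had a full 12 months (not stated), equal true healing of 60% in both groups could appear as a deficit of up to about 15 points for telemedicine. The planned Kaplan-Meier analyses of healing and revascularization are not biased by the cut-off, provided that enrolment date is unrelated to the outcome. The primary endpoint is not shown to be affected.

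**What to change.** 1. In section 5, state a last-enrolment date separate from the end of follow-up.
2. In the SAP, replace the crude proportion healed with one of the following, and apply the same horizon to any comparison group that is kept:
   - healing at a fixed horizon that every enrolled patient can reach, for example 6 months with last enrolment by 06/30/2021, which fits before 12/31/2021; or
   - the 12-month estimate from the Kaplan-Meier curve. The planned curve covers only telemedicine patients treated at UCD, so a comparison needs a matching estimate in the other group.

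The cost is a short amendment to section 5 and the SAP. There is no new procedure or extra contact, and the analysis date does not move. The first option gives a shorter-term outcome. The second gives a less precise 12-month estimate, because fewer patients are observed in the later months. Extending follow-up to 12 months after the last enrolment would also remove the problem, but it moves the analysis date and is not needed.

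### Death is not an endpoint, an end of follow-up or a contact item, so it cannot be told from loss to follow-up, and the amputation, healing and revascularization results cannot account for it.

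*Combined protocol and SAP*

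**What the plan says.** **Endpoints (Section 6).** The secondary list includes "time to wound healing, number of telemedicine visits, major amputation, number of hospitalizations, number of emergency room visits". Death and vital status do not appear there.

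**End of follow-up (Section 7, Follow-Up Post Telehealth Visit).** "Patients will be followed until they reach a secondary study end-point which is wound healing, amputation, or for a maximum of 12 months". Death is not among the stopping points.

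**Contact content (same paragraph).** "All patients will be contacted every 4 weeks to determine if they have had a procedure for their leg wound (revascularization"), and whether the wound has healed. Neither death nor amputation is named as something to ask about.

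**Contact channel (Section 4, exclusion criteria).** Patients without a home phone or home internet are excluded, because "This is needed to do follow up and any follow up telemedicine visits". The described follow-up therefore runs through the patient.

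**Analysis (Statistical Analysis Plan).** Secondary analyses are a chi-squared test on the proportion healed and "Kaplan-Meier analysis of time to definitive revascularization and wound healing for patients that underwent telemedicine and were treated at UCD". There is no analysis of major amputation, and no rule for censoring, missing data or competing events.

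**Elsewhere.** Section 8 deals only with patients who decline the activation questionnaire. Section 9 foresees only a breach of confidentiality. Neither covers patients who die or cannot be reached.

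**The concern.** The plan enrols adults with diabetes, arterial or vascular disease and a wound of more than two weeks, and follows them for up to a year. The Background names "lower socio-economic status, dialysis dependence, and older age" among the predictors of amputation. Those are not given as predictors of death, but they describe a population in which some deaths within a year are foreseeable.

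A patient who dies stops answering. Nothing written separates that silence from a move, a refusal or a changed number. Two things follow.

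- **Amputation.** A patient with no recorded amputation may be alive with the limb, dead with the limb, or dead after an amputation that occurred since the last contact. The three mean different things. If they are pooled, amputation-free status can be overstated.
- **Healing and revascularization.** A patient who dies can no longer heal or be revascularized. A Kaplan-Meier analysis that censors such patients treats them as still able to have the event. A competing-risk analysis needs the fact and date of death, which the plan does not collect.

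This information may not be recoverable once the project closes, so the gap cannot simply be left to the analysis stage.

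**Working it through.** **The plan's own figures.** The plan gives no mortality or amputation rate, so there is nothing on this point to reproduce. Its one design calculation is the power for time to specialty consultation: 24 patients, hazard ratio 3.0, historical median 9 weeks, event probability 0.44. Under an exponential model, 0.44 implies follow-up of −ln(0.56) × 9 / (3 × ln 2) = 2.5 weeks. The two-sided one-sample log-rank test then has power 0.894, against the stated 0.892, and 24 × 0.44 = 10.56, rounded to 11 events. That calculation reproduces and does not bear on this point.

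**Upper bound on the patients affected.** Input: 125 patients (Section 4). Assumption: 5% to 15% mortality over a full 12 months.

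- 125 × 0.05 = 6.25
- 125 × 0.15 = 18.75

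That is about 6 to 19 patients. It is a ceiling under these rates for two reasons. Follow-up stops at healing or amputation, so later deaths fall outside observation. Data collection ends on 12/31/2021 (Section 5), so anyone enrolled after 12/31/2020 cannot complete 12 months.

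**How the handling of deaths changes the answer.** Take constant, independent hazards, with 12-month risk *a* of amputation (absent death) and *d* of death (absent amputation), and ignore the stop at healing. Then:

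- λa = −ln(1 − a) and λd = −ln(1 − d)
- Alive and amputation-free: S = (1 − a)(1 − d)
- Amputation observed: A = (1 − S) × λa / (λa + λd)
- Death before any amputation: D = (1 − S) × λd / (λa + λd)
- No amputation recorded: 1 − A = S + D
- Kaplan-Meier amputation estimate with deaths censored: a, which exceeds A by a − A

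Example with a = 5% and d = 15%: λa = 0.0513, λd = 0.1625 and S = 0.95 × 0.85 = 0.8075. D = 0.1925 × 0.1625/0.2138 = 0.146, or 18.3 of 125. A = 0.1925 × 0.0513/0.2138 = 0.046.

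| a | d | Die first (of 125) | No amputation recorded | Alive and amputation-free | Kaplan-Meier excess, a − A |
|---|---|---|---|---|---|
| 5% | 5% | 4.9% (6.1) | 95.1% | 90.25% | 0.1 points |
| 5% | 15% | 14.6% (18.3) | 95.4% | 80.75% | 0.4 points |
| 5% | 25% | 24.4% (30.5) | 95.6% | 71.25% | 0.6 points |
| 20% | 5% | 4.5% (5.6) | 80.5% | 76.00% | 0.5 points |
| 20% | 15% | 13.5% (16.9) | 81.5% | 68.00% | 1.5 points |
| 20% | 25% | 22.5% (28.2) | 82.5% | 60.00% | 2.5 points |

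The gap between the fourth and fifth columns is D. Reading absence of amputation as amputation-free survival overstates it by 4.5 to 24.4 points over this grid, or by 4.5 to 14.6 points if mortality is held to 5% to 15%. Censoring deaths moves the amputation estimate the other way, by 0.1 to 2.5 points. All rates here are assumptions.

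For healing and revascularization, the same censoring puts the estimated proportion with the event at or above the true cumulative incidence. No size is given, because the documents supply no rate for either event.

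**The case against.** The strongest objection concerns the consequence. A reader might infer that a patient who dies is entered as having had no amputation, that a limb-safety result therefore looks better than it is, and that a telemedicine pathway with more deaths would look as safe as one with none. The documents do not support this.

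- No text says how dead or unreachable patients are coded. They might be censored, excluded or recorded as dead.
- Major amputation is a listed endpoint without a planned analysis, and no limb-safety result is defined. Section 8 says the project does not direct care.
- No comparison of pathways on amputation is planned. The SAP heading records removal of the comparison arm, and the between-group wording that remains covers only specialty visit and healing.
- The direction is not fixed. With complete ascertainment, the crude proportion is the correct cumulative incidence of amputation. With deaths censored, Kaplan-Meier makes amputation look slightly worse.
- Setting an amputation rate beside a rate of amputation or death compares two different endpoints. The difference is not in itself a bias.

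It is also fair to say that hospitalizations, emergency visits and amputation are endpoints the 4-weekly contact does not name, so some other source must be intended. That source might reveal deaths.

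All of this stands against the stronger reading. It does not fill the gap. Death is absent in all three places, no other source is described, and the Kaplan-Meier analyses that are planned do need to know who died and when.

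**Conclusion.** The omission can be read directly from Sections 6 and 7, and neither the SAP nor any other section repairs it. Followed as written, the plan cannot separate death from loss to follow-up. Absence of major amputation therefore cannot be read as limb salvage, and the healing and revascularization curves cannot account for death.

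The size is unknown. At an assumed 5% to 15% mortality over a full year, the ceiling is about 6 to 19 of 125 patients. The documents do not establish a favourable bias in the amputation result: amputation-free status can be overstated, but the direction and amount depend on a handling rule that has not been written. The judgement that some deaths will occur rests on the population enrolled, and not on a figure in the documents.

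**What to change.** 1. Section 6: add death, with its date, to the secondary endpoints.
2. Section 7: add death to the events that end follow-up. When a patient cannot be reached, check vital status through the referring rural clinic or the medical record before recording loss to follow-up.
3. SAP: report major amputation or death (amputation-free survival) beside major amputation. Because follow-up stops at healing, state that both describe the period up to that point.
4. SAP: estimate healing and revascularization by cumulative incidence with death as a competing event, and state separately how patients lost to follow-up are handled.

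The cost is wording in two sections and the SAP, a date to record, and occasional record checks or calls to the referring clinic. The documents do not describe staffing or a contact form, so that effort cannot be priced from them. No visits or procedures are added and patient care does not change. The composite figure will look less favourable than amputation alone, which should be explained when it is reported.
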